## 1. Background

In recent years, the treatment of intracranial aneurysms has shifted from a primarily surgical paradigm to one of endovascular management. The International Subarachnoid Aneurysm Trial (ISAT), published in 2002, demonstrated improved mortality and dependency rates at 1-year in those undergoing endovascular coil embolization to those undergoing clipping. However, follow-up data from the ISAT revealed a higher incidence of late re-bleeding and recurrence among aneurysms treated via embolization compared to clipping. The difficulties with recurrence have been relatively consistent in the literature, with an estimated angiographic recurrence rate of approximately 10-20% (although as high as 33% in one study); fortunately, however, the re-bleed rate has consistently been very low. In light of these factors, many institutions have shifted towards endovascular management, and close follow-up to detect recurrence, with surgical clipping as a secondary option for specific patients or those who fail endovascular means.

Larger aneurysms have demonstrated higher hemorrhage rates when observed in longitudinal studies. Similarly, larger aneurysms are more difficult to treat successfully via coil embolization; initial and long-term occlusion is inversely related to aneurysm size. Smaller aneurysms are generally easier to obtain satisfactory packing density and occlusion while giant aneurysms are much more challenging and plagued by high recanalization rates. For this reason, studies of small aneurysms usually demonstrate uniformly excellent results while studies of large or giant aneurysms usually demonstrate poor long-term results. Therefore, mid-sized aneurysms (6-14 mm) likely represents the optimal study group for evaluating true differences between coiling treatments.

A major focus of clinical research has been improving aneurysm occlusion and recurrence rates through modification of techniques, devices and embolic materials. Until recently, bare platinum detachable coils, which are biologically inert, had been the mainstay for neuro-interventionists. The first bioactive coil approved by the U.S. Food and Drug Administration, the Matrix coil (Stryker), has only modest evidence supporting its use. More recent bioactive and non-bioactive coils, including hydrogel and Cerecyte coils, have more robust evidence supporting their use. Both types of coil have recently completed evaluation in large, prospective randomized trials. Promisingly, the unpublished data suggests excellent aneurysm occlusion rates; however, the primary endpoints of both studies were not statistically different compared to bare platinum coils. Although it is apparent that occlusion rates have improved since the initial ISAT data, new coil designs have yet to demonstrate superiority over bare platinum coils in a randomized controlled trial.

Considerable emphasis has been placed on the volumetric filling of aneurysms, or ‘packing density’, which has been related to long-term outcome. Packing density of 20-30% has been suggested as being the desired packing to ensure stable occlusion, however achievement of densities exceeding 25% can be difficult in aneurysms larger than 5mm. The use of framing coils, or large-diameter coils initially placed into the aneurysm to serve as a foundation for the placement of smaller-diameter “filling” coils, has demonstrated efficacy in

case series. Framing platinum coils of larger diameter are resistant to deformation regardless of flow rate in a flow-model, unlike smaller-diameter framing coils which became unstable as flow rate increases. These studies suggest that larger diameter platinum coils may be more stable during and after endovascular aneurysm coil embolization, and that smaller-diameter framing coils may have a higher propensity towards recanalization. It should be noted that, contrary to the name, current “Eighteen” platinum coils produced by Stryker (Natick, MA) are actually 0.014-0.0155 inches in size. These coils are larger than standard coils, which are usually sized 0.010 or 0.012”.

## **2. Purpose and Hypothesis**

**2.1 Purpose:** To compare angiographic outcomes in patients receiving 0.014-0.0155” platinum framing and filling coils followed by further aneurysm filling and finishing with less than 0.014” bare platinum coils (as deemed appropriate by the treating physician), versus those treated solely with coils less than 0.014”.

**2.2 Hypothesis:** Angiographic occlusion on follow-up imaging will be more frequent in patients receiving 0.014-0.0155” platinum coils during embolization compared to those receiving smaller-diameter coils.

## **3. Objectives**

### **3.1 Primary Outcome**

Occlusion rate: Angiographic occlusion, improvement or no change in the post-coiling appearance of the aneurysm as judged by an independent core lab on follow-up angiography at 12-18 months after endovascular embolization.

### **3.2 Secondary Outcomes**

1. Treatment related morbidity and mortality, as measured by the NIH Stroke Scale
2. Packing density as measured by volumetric filling of the aneurysm
3. Clinical outcome at 3-6 and 12-18 months post-coiling, as measured by the modified Rankin Scale
4. Re-hemorrhage and re-treatment rates

## **4. Trial Design**

FEAT will be a prospective, randomized trial comparing the utilization of 0.014-0.0155” coils versus smaller diameter coils in mid-sized aneurysm treatment. The 0.014-0.0155” bare platinum coils (Stryker, Natick, MA) are FDA-approved and in common use at institutions in this country and across the world. Patients will be enrolled who meet the inclusion criteria and consent to participate. Patients will be randomly assigned by a central web-based system in a 1:1 manner to either the framing coil treatment or the non-framing coil treatment. Data on each patient will be collected at the time of enrollment and treatment, and at first and second follow-up visits.

### **4.1 Inclusion Criteria**

1. Patient presenting with ruptured or unruptured cerebral aneurysm appropriate for endovascular treatment as determined by the neurovascular treating team (neurointerventionist and/or neurosurgeon).
2. The neurointerventionist feels that the aneurysm can be safely treated with either using, or not using, a 0.014-0.0155” platinum coil.
3. Patient is 18-80 years of age (inclusive).
4. Patient is Hunt and Hess grade 0 to 3.
5. Patient has given fully informed consent to endovascular coiling procedure. If the patient cannot provide self-consent, appropriate written consent has been sought from their authorized surrogate or appropriate power of attorney.
6. Aneurysm is 6-14 mm in maximum diameter.
7. Patient is willing and able to return for clinical evaluation and follow-up imaging evaluation (angiography or MRA) at 3-6 months and 12-18 months after endovascular treatment.
8. The patient has not been previously randomized into this trial or another conflicting/confounding trial.
9. The aneurysm has not been previously treated by coiling or clipping.

## **4.2 Exclusion Criteria**

1. Patient has more than one aneurysm requiring treatment in the current treatment session, and only one of those to-be treated aneurysms fits the FEAT inclusion criteria (i.e., - if either (1) a patient has multiple aneurysms, but only one will be treated at enrollment; or (2) if two or more aneurysms are treated during the current treatment session and BOTH are able to be enrolled, then they remain eligible for the trial. Non-treated additional aneurysms may be treated at a later date with any coil type that the operator chooses).
2. Target aneurysm has had previous coil treatment or has been surgically clipped.
3. Hunt and Hess score is 4 or 5 after subarachnoid hemorrhage.
4. Inability to obtain informed consent.
5. Medical or surgical co-morbidity such that the patient's life expectancy is less than 2 years.

Death or procedural/disease-related morbidity may result in some subjects not having follow-up angiography. For the primary outcome of angiographic recurrence, the analysis will be conducted 2 ways: (1) among only those patients with angiographic assessment at 12-18 months, and (2) among patients with angiographic assessment, plus those with death or procedural/disease-related morbidity that precluded angiography, with such patients counted as incident events. Similarly, for the secondary outcome of treatment-related morbidity and mortality, patients without angiographic evaluation due to death or procedural/disease-related morbidity will be counted as incident events in the analysis.

Use of coil-assist devices (stent, balloon, etc.) will be allowed. Intention to use such a device will be recorded pre-procedure, along with dome to neck ratio and rupture status.

Additional critical components of the study design include the large number of patients required to demonstrate a statistically significant difference, and the subsequent significant length of time required to allow enrollment. Therefore, we propose a three phase study design to address the following concerns:

- 1) A 6-year time window renders any conclusions irrelevant due to progress in technology. Typically the conclusions of long-term studies in the endovascular space are called into question because they do not include technology that is considered modern by the time the study is completed. Stryker has multiple coil iterations planned over the next 5 years. To not involve these new technologies would make the study non-viable to

Stryker and irrelevant to current practice by the time it was completed. However, any incorporation of iterative technology needs be done in a regimented manner to ensure it does not affect the fundamental study question.

2) There is an onus on the medical and device industry community to provide quality timely short/mid-term data on new technologic advances.

3) All parties would like to complete the study with a concrete scientific conclusion that has legitimate and credible conclusions that move forward our understanding of this complex disease process and its methods of treatment. Unfortunately, a series of multiple underpowered studies obviates this process.

These concerns create an overarching need to perform a scientifically valid study that develops our knowledge base in a statistically valid way, while simultaneously generating much needed early data on new product benefit and to provide useful medium-term knowledge to guide physician practice and industry product development.

To address these concerns the investigative design will be one contiguous study completed in three phases. The theme across all phases will remain true to the fundamental study design question, “Does use of larger diameter framing coils improve treatment durability?” However, the phases will be introduced to allow controlled involvement of developing technologies and, as a result, an avoidance of the above noted concerns. Stryker products will be used in both arms of the trial (18 plus non-18 versus non-18 only) to minimize potential differences from other coil design variables. To ensure progressive relevance and to generate critical short-term technology evaluations the study will be divided into three phases:

- Phase I: GDC 18 as deemed appropriate plus current Stryker 10 coils (including Target) versus current Stryker 10 coils (including Target);
- Phase II: Target XL as deemed appropriate plus all Target versus all Target;
- Phase III: Future generation of Target coils as deemed appropriate plus all Target versus all Target.

This study design will allow a number of important improvements over typical long term endovascular studies:

1) A valid statistical analysis of the benefit of large diameter coil size in aneurysm treatment, with other variables removed as only Stryker coils will be used in both cohorts and there will be a consistent number of newly developing Stryker technologies on both sides of the treatment/control arm equation. Upon completion of the trial a legitimate scientific question can be answered with statistical validity.

2) Short/mid-term technology evaluations will be generated on iterative advances in coil technology. At the completion of each phase, the non-18 arm descriptive statistics will be analyzed and reviewed so as to provide short-term critical feedback about the developing technology. This will only be performed for the non-18 arm in order to avoid any potential statistical penalties in the analysis of the primary hypothesis.

3) Data will have relevance to current practice upon completion as it will reflect inclusion of evolving technology.

4) Long-term comparisons of progress over time will be able to be made across phases.

## **5. Treatment Protocol**

### **5.1 Methods**

#### 5.1.1 Clinical methods

1. Patients randomized to the framing treatment arm will have an initial 0.014-0.0155” framing coil placed. Following this coil, additional 0.014-0.0155” framing coils may be placed, in a “Russian doll technique”, and as recommended, until the treating physicians deem, in their best clinical judgment, that a transition to smaller, 0.010” or 0.012” bare platinum coils, is appropriate. Following placement of the primary framing coil (per the randomization assignment), further coil placement is at the treating physician’s clinical discretion, until satisfactory aneurysm occlusion is obtained. However, treating physicians are encouraged to use as many 0.014-0.0155” framing coils as they determine are safe and clinically appropriate. Patients randomized to the control arm will have bare platinum coils less than 0.014” placed into the aneurysm only, under the operator’s discretion, until satisfactory aneurysm occlusion is obtained.

2. Coiling of aneurysms will be performed according to the standard of care at each institution. Choice of catheters, guide wires and other devices will not be dictated. However, non-bare-platinum coils, such as bioactive or hydrogel coils, may NOT be used in this protocol.

3. For ruptured aneurysms, the use of heparin and anti-platelet agents and the timing of their use will be according to treating physician preference.

4. For unruptured aneurysms, use of and choice of anti-platelet agents will be according to treating physician preference and local standard of care.

5. If, during the course of the procedure, the operator determines that it would be safer to use other coils or devices, such as bioactive or hydrogel coils, patient safety should take precedence over the randomly assigned treatment protocol. Reasons for protocol deviations, which are anticipated to be infrequent, will be recorded in the eCRF.

#### 5.1.2 Research methods

1. Investigators should only randomize patients if they believe they can actually treat the patient equally safely and effectively regardless of the presence or absence of a 0.014-0.0155” platinum coil(s).

2. As far as possible, the intention is to exclusively use 0.014-0.0155” bare platinum coils for the initial coil in the Eighteen coil treatment arm and for as many subsequent coils as safe and appropriate, as determined by the treating physician. However, if for any reason a treating physician needs to forego placement of a 0.014-0.0155” coil or use a different coil for this purpose, the patient will remain in the study according to the intention to treat principle. Conversely, in patients assigned to the non-Eighteen coil treatment arm, no 0.014-0.0155” platinum coil is to be placed. However, if for any reason the treating physician determines he/she needs to place a 0.014-0.0155” bare platinum coil, the patient will remain in the study according to the intention to treat principle.

3. JPG’s of de-identified images will be uploaded for independent evaluation and stored in the study’s electronic database. These images will be reviewed by an independent, blinded core lab.

4. An electronic case report form (eCRF) will be completed at the end of the procedure. The procedural details collected for the eCRF will include findings of angiographic anatomy, size, location, neck size and dome-to-neck ratio .

5. At time of discharge, any adverse events will be recorded on the eCRF.

6. Data on any further aneurysm treatment or re-treatment of the study treated aneurysm will be collected during the study period.

#### 5.1.3 Follow-up

1. The following assessments will be performed at each standard care follow-up visit (3-6 months and 12-18 months post-coiling): (1) clinical outcome; (2) follow-up angiography/MRA; (3) modified Rankin Score; (4) NIH Stroke Scale.

2. The assessment window allowed for each follow-up visit is as follows: (1) 3-6 month follow-up allowable window is 3-7 months post-coiling; (2) 12-18 month follow-up allowable window is 10-20 months post-coiling.

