#### 3.1.1 Study Duration and Time Points

All patients will be followed for 12 to 18 months post-procedure. Endpoints will be measured at discharge from the index procedure, 3 to 6 months post-procedure, and 12 to 18 months post-procedure. The 3 to 6 month visit and 12 to 18 month visit align with standard of care visits.

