#### 5. STUDY ENDPOINTS

##### **5.1 Primary Endpoint**

The primary endpoint is angiographic occlusion at 12 to 18 months post-randomization as measured by a Raymond score of 1 or 2 (adequate occlusion). Patients' angiograms for the 3 to 6 month visit, the 12 to 18 month visit, and any clinically driven angiogram taken prior to 18 months post-randomization or study exit will be considered for angiographic occlusion. If any of these angiograms show inadequate angiographic occlusion (Raymond score >2), the patient will be considered to have inadequate occlusion at the 12 to 18 month visit and be considered a treatment failure.

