### 6.5.3 *Missing Primary Endpoint Data*

Patients without previous evidence of inadequate angiographic occlusion, either on the 3 to 6 month visit angiogram or on a clinically driven angiogram taken prior to study exit, that miss the 12 to 18 month angiogram, or whose 12 to 18 month angiogram is not readable by the core lab, will be missing the primary endpoint. Patients missing the primary endpoint who die prior to or during the 12 to 18 month visit window (up to 18 months post-randomization) and die with known cause of death related to their aneurysm or unknown cause of death will be considered treatment failures with inadequate occlusion. Patients missing the primary endpoint with a known cause of death unrelated to their aneurysm will be considered missing.

Patients with missing primary endpoint data will have their 12 to 18 month angiographic

occlusion status imputed via multiple imputation assuming that the data are missing at random. The imputation model will be stratified by randomization assignment and include age, sex, randomization strata for aneurysm status, randomization strata for wide neck status, aneurysm size, and angiographic occlusion status at the 3 to 6 month visit. Since this model includes a mixture of variables types (i.e. continuous and binary), a fully conditional specification method will be used (Berglund 2014).

The main feature of the imputation approach is the creation of a set of clinically reasonable imputations for angiographic occlusion for each patient with missing data. This will be accomplished using a set of repeated imputations created by predictive models based on the majority of participants with complete data. The imputation models will reflect uncertainty in the modeling process and inherent variability in patient outcomes, as reflected in the complete data. Thirty datasets will be imputed.

After the imputations are completed, all of the data (complete and imputed) will be combined and the analysis performed for each imputed-and-completed dataset. Rubin's method of multiple (i.e., repeated) imputation will be used to estimate treatment effect (Rubin 1986).

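### The protocol accepts the final visit up to 20 months after coiling, but the SAP stops counting aneurysm deaths as failures at 18 months after randomization and does not say which final scans count

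*Combined protocol and SAP*

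**What the plan says.** Protocol 5.1.3 sets the tolerance for the last visit: "12-18 month follow-up allowable window is 10-20 months post-coiling". The clock starts at coiling.

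The SAP does not mention that tolerance. Its section 5.1 reads "The primary endpoint is angiographic occlusion at 12 to 18 months post-randomization", so the clock starts at randomization. SAP 3.1.1 uses the procedure instead: "All patients will be followed for 12 to 18 months post-procedure".

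For deaths without a primary endpoint, SAP 6.5.3 assigns failure when the cause is aneurysm-related or unknown and the patients "die prior to or during the 12 to 18 month visit window (up to 18 months post-randomization"; the bracket closes the window at 18 months. Patients whose endpoint is missing have it "imputed via multiple imputation assuming that the data are missing at random".

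For unscheduled imaging, SAP 5.1 admits "any clinically driven angiogram taken prior to 18 months post-randomization or study exit", while SAP 6.5.3 refers to evidence of failure "on a clinically driven angiogram taken prior to study exit", with no 18-month limit.

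Protocol 4.2, in the second of its two primary analyses, counts deaths that prevented angiography as events and sets no 18-month limit.

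**The concern.** The protocol keeps the final visit open for up to two months after the SAP's death rule has closed. A patient can still be on schedule for the last scan, die of the aneurysm before it, and fall outside the rule that makes such a death a failure. Nothing else in SAP 6.5.3 catches that patient. The other death rule covers only known unrelated causes, so the endpoint is simply missing and goes to imputation. A known bad outcome is then replaced by a draw that usually comes out as success.

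The same mismatch leaves a second question open. The SAP gives no rule for mapping scan dates to visits. For a core-lab reading at, say, 10.5 or 19 months, the analyst must decide whether it supplies the primary endpoint or is set aside and imputed. That choice should be fixed before the data are seen.

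**Working it through.** **1. Windows side by side**

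| Item | Limit | Clock starts at | Source |
|---|---|---|---|
| Final visit, allowable | 10–20 months | coiling | Protocol 5.1.3 |
| Follow-up duration | 12–18 months | procedure | SAP 3.1.1 |
| Primary endpoint | 12–18 months | randomization | SAP 5.1 |
| Death counted as failure | up to 18 months | randomization | SAP 6.5.3 |
| Clinically driven scan | before 18 months, or study exit | randomization | SAP 5.1 |
| Clinically driven scan | before study exit | not stated | SAP 6.5.3 |

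The protocol window is 20 − 10 = 10 months wide and the SAP's is 18 − 12 = 6. Four months lie outside the SAP's: two early (10–12) and two late (18–20). This ignores the gap between randomization and coiling, for which no maximum is given.

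**2. Late deaths**

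Consider an aneurysm-related or unknown-cause death at 18–20 months, with no final scan and no earlier failing scan. Under SAP 6.5.3 it is not a failure, so it is missing and imputed. With the planning rates of SAP 6.5.2 (73% and 82%) standing in for the imputation model, it becomes a success with probability of roughly 0.73 to 0.82.

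Let 73% and 82% be the rates when these deaths count as failures, with 325 per arm and k such deaths in an arm. Imputing them at the rate of the remaining patients gives p × 325 / (325 − k). The successes are 0.73 × 325 = 237.25 and 0.82 × 325 = 266.5. The reference risk ratio is 0.82 / 0.73 = 1.123. The documents give no late-death rate, so every k is an assumption.

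| Deaths, control / larger coil | Control | Larger coil | Risk ratio |
|---|---|---|---|
| 3 / 3 | 237.25/322 = 73.7% | 266.5/322 = 82.8% | 1.123 |
| 3 / 1 | 237.25/322 = 73.7% | 266.5/324 = 82.3% | 1.116 |
| 1 / 3 | 237.25/324 = 73.2% | 266.5/322 = 82.8% | 1.130 |
| 5 / 2 | 237.25/320 = 74.1% | 266.5/323 = 82.5% | 1.113 |
| 2 / 5 | 237.25/323 = 73.5% | 266.5/320 = 83.3% | 1.134 |

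Success rises in both arms. The risk ratio moves only when the counts differ, and it can move either way.

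**3. Scans, if the strict reading were applied**

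The plan's own figure comes first. SAP 6.5.2 claims about 80% power at 325 per arm for 73% against 82%, two-sided 0.05. With pooled variance under the null:

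power = Φ[(0.09√n − 1.96√(2p̄(1 − p̄))) / √(p₁(1 − p₁) + p₂(1 − p₂))]

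Here p̄ = 0.775, √(2 × 0.775 × 0.225) = 0.5906 and √(0.1971 + 0.1476) = 0.5871. At n = 325 this is Φ[(1.6225 − 1.1575)/0.5871] = Φ(0.792) = 78.6%, which agrees with the stated approximate figure.

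If a share m of endpoints became missing, then n = 325(1 − m):

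| Assumed m | n per arm | Power |
|---|---|---|
| 0% | 325 | 78.6% |
| 5% | 308.75 | 76.5% |
| 10% | 292.5 | 74.2% |
| 20% | 260 | 69.2% |

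These are complete-case values. The SAP's imputation model uses occlusion status at 3–6 months and could recover part of the loss.

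**The case against.** The strongest reply concerns the scans. SAP 5.1 takes the angiograms belonging to the two named visits, and SAP 6.5.3 defines missingness as not having a readable angiogram for the last visit. Both go by visit label, not by date. Protocol 5.1.3 says what that label covers, so a scan at 10.5 or 19 months can fairly be called the final-visit scan and is then not missing. The 18-month phrase in SAP 5.1 most naturally attaches to clinically driven scans only. This stands: the text is ambiguous and does not establish that readings are lost. The strict reading keeps some support from the opening sentence of SAP 5.1 and from the bracket in SAP 6.5.3.

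A reader might also infer that 40% of final scans fall outside the SAP window, since four of the ten allowed months do. That requires scans spread evenly over 10–20 months. Both documents schedule the visit at 12–18 months and treat the wider range as tolerance, so they do not support the figure.

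A reader might infer that a failing clinically driven scan at 18–20 months is always ignored. SAP 5.1 adds study exit as an alternative limit and SAP 6.5.3 names only study exit. The SAP is inconsistent here, not uniformly closed at 18 months.

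Finally, the deaths at issue need a particular cause, a two-month interval, no final scan and no earlier failure. They are likely to be rare. That limits the size of the problem but does not make the rule right.

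**Conclusion.** The two documents conflict in their current text. The firm part is the death rule: an aneurysm-related or unknown-cause death at 18–20 months, before the final scan and without earlier failure, is imputed under missing at random instead of counted as a failure. Its effect is probably small. It inflates success in both arms and shifts the risk ratio only if such deaths are unequal, for example from 1.123 to 1.113 with an assumed 5 against 2.

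Loss of early or late final scans is possible, not established. The power figures of 76.5, 74.2 and 69.2% depend on the strict reading, on assumed shares of 5, 10 and 20%, and on a complete-case analysis.

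It would be tempting to conclude that the mismatch biases the whole analysis toward success. The documents support that direction for the late deaths only; nothing in them shows that imputing in place of early or late scans would favor success.

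The inconsistent limit for clinically driven scans and the mixed time origins are real drafting faults. Their numerical effect cannot be computed, because the documents give neither scan timing nor the interval from randomization to coiling.

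**What to change.** Before data lock, which the SAP's purpose statement allows, reconcile Protocol 5.1.3 with SAP 3.1.1, 5.1 and 6.5.3:

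- Use one time origin for visits, scans and deaths.
- State that every scan the protocol accepts as the final visit, and that the core lab can read, supplies the primary endpoint.
- End the death rule in SAP 6.5.3, and the clinically driven scan rule in SAP 5.1 and 6.5.3, at the same upper limit as the protocol's final-visit window.

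The cost is SAP wording only. No extra data, sample size, change to the visit schedule or change to clinical management is involved.
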